3 OBJECTIVES

The primary objective is to evaluate the diagnostic accuracy of maternal venous lactate measurement in addition to maternal vital signs (at Day 0 and/or Day 1), in maternal sepsis in low-resource health facility settings in Malawi, Uganda and Pakistan.

Secondary objectives are to:

• evaluate the immediate diagnostic value of lactate testing at Day 0 in addition to maternal vital signs in maternal sepsis at Day 0 (reference standard at Day 0 only);

- assess the short-term predictive value of lactate testing at baseline, in addition to vital signs, for maternal sepsis at 24-hours (24-hour reference standard) in those without sepsis at baseline;
- explore if baseline venous lactate, in addition to vital signs, improves prediction of severe morbidity and mortality from infection;
- explore if the diagnostic accuracy of lactate in addition to maternal vital signs alone, varies by the pre-specified subgroups of pregnancy status (pregnant or post-delivery / post miscarriage / post-abortion), source of sepsis (genital tract or non-genital tract) and condition on admission (stable or critical);
- examine the effect of adjusting the threshold values for lactate assessment on the sensitivity and specificity of the index tests;
- explore the use of an alternative reference standard in which the Sequential Organ Failure Assessment (SOFA) score is modified to use maternity specific ranges for creatinine and platelet concentration.

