4.2 ELIGIBILITY

Inclusion criteria:

- 1. Women pregnant or within 6 weeks of the end of the pregnancy.
- 2. Women with a suspected or confirmed infection requiring in-patient care:
 - A. Any suspected or confirmed infection with or without organ-dysfunction.
 - B. Any clinical signs suggestive of infection (e.g., fever).
 - C. Request for any bodily fluid culture (blood, urine, cerebrospinal fluid, etc.) or swab specimens (nasopharyngeal, oropharyngeal, vaginal, endocervical) for the diagnosis of suspected infection (not routine sampling e.g., routine COVID-19 screening).
 - D. Non-prophylactic use of antibiotics or other antimicrobial drugs at admission or during hospital stay.
 - E. Any procedure for treatment of a suspected infection (e.g., wound exploration, evacuation of the uterus, laparotomy, etc.).
 - F. Any unexplained organ-dysfunction (i.e., organ dysfunction not attributable to an underlying cause).
- 3. Estimated age \geq 16 years.
- 4. Willing to provide a signed (and witnessed, if applicable) informed consent form.

- 5. Willing to be contacted if necessary.
- 6. Willing to have additional blood samples taken.

Exclusion criteria:

- 1. Women In active labour or within 2 hours of delivery are excluded as lactate is expected to be elevated by labour and childbirth.
- 2. Women with any non-severe, localised, or chronic infection (TB, HIV) or colonization (GBS).
- 3. Women undergoing only treatment with prophylactic antibiotics (for procedures, GBS).

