5.4 OUTCOME DEFINITIONS

The primary outcomes are the absolute differences in sensitivity and specificity between pairs of index tests: vital signs (Day 0) vs vital signs (Day 0) + lactate (Day 0), and vital signs (Day 0) + lactate (Day 0) vs vital signs (Day 0 and Day 1) + lactate (Day 0 and Day 1).

Secondary outcomes include:

- The absolute differences in sensitivity and specificity between vital signs (Day 0) alone and vital signs (Day 0) + lactate (Day 0) for maternal sepsis assessed at Day 0 only;
- The predictive value of vital signs (Day 0) alone compared to that of vital signs (Day 0) + lactate (Day 0) in those without sepsis at baseline, for maternal sepsis assessed at Day 1 only;
- The predictive value of vital signs (Day 0) alone compared to that of vital signs (Day 0) + lactate (Day 0) for the occurrence of severe morbidity and mortality from infection (WHO "severe maternal outcomes") (4), which is assessed daily until day 14 or discharge or death, if sooner;
- The sensitivity and specificity of vital signs (Day 0) + lactate (Day 0) and vital signs (Day 0 and Day 1) + lactate (Day 0 and Day 1) by: pregnancy status (pregnant or postdelivery/post miscarriage/post-abortion), source of sepsis (genital tract or nongenital tract) and condition on admission (stable or critical);
- The sensitivity and specificity of the primary index test comparisons including those women discharged early, assuming that they did not have sepsis;
- In an exploratory analysis, the sensitivity and specificity of each index test will be estimated based on different threshold values for lactate;
- To explore the use of an alternative reference standard, in which the SOFA score is modified to use maternity specific ranges for creatinine and platelet concentration, an independent expert review group will examine all cases with discordant results to adjudicate based on clinical features, clinical management, response to treatment and outcomes, if the case fitted the WHO definition of maternal sepsis. The pattern of discrepant results will be investigated descriptively.
 - 5.5 SAMPLE SIZE

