7.3 FINAL ANALYSIS

Primary analysis

We will estimate the sensitivity, specificity, positive predictive value (PPV) and negative predictive value (NPV) of the three index tests to detect sepsis assessed at Day 0 and Day 1. The 95% CIs for the estimates will be calculated using the Wilson method for proportions. To compare the accuracy of sepsis diagnosis by vital signs alone versus vital signs + lactate, we will fit separate generalized estimating equation (GEE) models for women with and without sepsis to estimate absolute differences in sensitivity and specificity, respectively. This approach exploits the paired nature of the data. We will compute absolute differences

in sensitivities and specificities from the GEE models using a post-estimation procedure with Cls computed using the delta method.

Secondary analyses

We will assess (a) index tests based on Day 0 only against Day 0 reference standard to determine immediate diagnostic value; (b) index tests based on Day 0 only against Day 1 reference standard in those without sepsis at baseline to determine short-term predictive value; and (c) index tests based on Day 0 only with occurrence of infection related "severe maternal outcome" (near miss or maternal mortality) (4) prior to hospital discharge to determine predictive value for severe morbidity or mortality (5) assuming that those women discharged prior to the Day 1 assessment did not have sepsis. Sensitivity, specificity, PPV, and NPV will be calculated for each test. In addition, for each of the analyses above, we will estimate absolute differences in sensitivity and specificity of vital signs alone versus vital signs (Day 0) + lactate (Day 0).

Pre-specified subgroup analyses will include pregnancy status (pregnant or postnatal) and illness severity to explore if the test accuracy of lactate in addition to vital signs alone varies by these subgroups.

Exploratory receiver operating characteristic (ROC) curve analyses will examine the effect of adjusting the threshold value for lactate on the sensitivity and specificity of the index tests.

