Appendix 1: Table of assessments

ASSESSMENT		DAYS IN STUDY													
	Screening		Week 1				Week 2								
Face to face	D0	D1	D2	D3	D4	D5	D6	D7	D8	D9	D10	D11	D12	D13	D14
Study participation															
Eligibility	x														
Informed consent	X														
Eligibility confirmed	X														
Baseline data collection	x														
Vital signs	x	x	x	x	x	x	X	x	х	x	X	X	X	X	X
Medications and fluids	X	x	x	x	x	x	X	x	Х	x	X	X	X	Х	X
Escalation of care	X	x	x	X	x	x	X	Х	Х	x	X	X	X	Х	X
Maternal near-miss criteria assessment	x	x	x	x	x	x	x	х	Х	x	X	X	X	X	X
Blood Sample															
Lactate sample 1 Day 0 (blinded)	X														
Lactate sample 2 Day 1 (22-36 hours) (blinded)		x													
Study completion															
Study completion form															X

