Appendix 2: Maternal "near misses"

Status
Brain conditions
Unconscious for more than 12 hours
Stroke
Status epilepticus or uncontrolled fits
Clotting and bleeding
Failure to form clots (clinically absence of clotting from an IV site or suture after 7
minutes, or bedside clotting test taking more than 7 minutes)
Transfusion of more than 2 units of blood
Platelets of less than 50*10^3/µL
Heart conditions
Cardiac arrest
Cardiopulmonary resuscitation
Shock (persistent systolic blood pressure less than 80mmHg with pulse more than
120 beats per minute)
Use of continuous vasoactive drugs e.g. adrenaline infusion
Kidney conditions
Oliguria (urine output less than 30ml/h for 4 hours or less than 400ml/24 hours) not responsive to fluids
Creatinine greater than 300 $\mu mol/L$ or 3.5mg/dL
Dialysis
Liver conditions
Bilirubin more than 100 µmol/L or 6.0 mg/dL
Lung conditions
Cyanosis
Gasping
Respiratory rate more than 40 or less than 6 breaths per minute
Low oxygen saturations of less than 90%% for more than 1 hour
Need for ventilation (not due to anaesthesia)
Uterus conditions
Laparotomy other than for caesarean section or ectopic pregnancy
Hysterectomy due to infection or haemorrhage
Uterine rupture

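### SAP 7.3(c) claims predictive value for severe maternal outcome but neither excludes women already in near-miss at Day 0 nor starts the outcome after the index test

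*SAP*

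**What the plan says.** - **Objective (SAP 3).** The aim is to "explore if baseline venous lactate, in addition to vital signs, improves prediction of severe morbidity and mortality from infection".
- **Analysis (SAP 7.3).** The Day 0 tests are set against the outcome as "c) index tests based on Day 0 only with occurrence of infection related" severe maternal outcome (near-miss or death), "prior to hospital discharge to determine predictive value for severe morbidity or mortality". The one added condition concerns women discharged before the Day 1 assessment, who are assumed not to have had sepsis. It does not address women already in near-miss at Day 0.
- **Neighbouring analysis (SAP 7.3(b)).** The Day 1 prediction is made "in those without sepsis at baseline to determine short-term predictive value".
- **Outcome window (SAP 5.4).** Severe maternal outcome is one "which is assessed daily until day 14 or discharge or death, if sooner". An end is given but no start.
- **Schedule (Appendix 1).** The row "Maternal near-miss criteria assessment" is marked on every day from D0 to D14.
- **Population (SAP 4.2 and 3).** Eligibility covers "Any suspected or confirmed infection with or without organ-dysfunction", and critical condition on admission is a planned subgroup.
- **Criteria (SAP 5.2 Table 1 and Appendix 2).** Vital signs are positive if any one threshold is crossed: respiratory rate >25, heart rate >120, systolic pressure <90, low urine output or altered mental state. The near-miss list includes respiratory rate >40 or <6, and "Shock (persistent systolic blood pressure less than 80mmHg with pulse more than" 120.

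**The concern.** A prediction analysis needs the outcome to follow the test. If a woman meets a near-miss criterion when her Day 0 vital signs are taken, a positive test recognises her present state and says nothing about later risk. For some criteria it is close to the same reading used twice. The plan takes care of this in (b) but not in (c), although both are described as predictive and both use the Day 0 tests.

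What is at stake is the answer to one secondary, exploratory objective: whether lactate adds to vital signs in identifying women who will go on to severe morbidity or death. A mixture of concurrent recognition and later prediction does not answer it, and the published figures would not show how much of each they contain.

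**Working it through.** **Step 1. Can Day 0 near-misses enter the outcome?** Women with organ dysfunction are eligible (4.2), critical admissions are expected (3), near-miss is assessed at D0 (Appendix 1), and neither 5.4 nor 7.3(c) sets a start or an exclusion. Under the text as it stands they enter.

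**Step 2. Which criteria share a variable with the index test?**

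| Appendix 2 criterion | Table 1 threshold | Relation |
|---|---|---|
| Respiratory rate >40 | >25 | Wholly inside |
| Respiratory rate <6 | >25 | Not inside |
| Shock: systolic <80 with pulse >120 | <90; >120 | Wholly inside both, but must be persistent |
| Unconscious >12 hours | Altered state | Related; needs duration |
| Oliguria: <30 ml/h for 4 h, or <400 ml in 24 h, unresponsive to fluids | <0.5 ml/kg/h | Overlaps; needs duration |

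Most other entries (for example stroke, transfusion, creatinine, bilirubin, hysterectomy) use no Table 1 variable. So vital signs are positive by construction for respiratory rate >40, and for systolic <80 with pulse >120 when present at the Day 0 reading.

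**Step 3. Effect on sensitivity.** The SAP states no event rate, accuracy or sample size for (c), so there is no figure to reproduce. Let f be the share of outcomes already present at Day 0. Then

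reported sensitivity = f × S_prevalent + (1 − f) × S_incident,

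and the excess over S_incident is f × (S_prevalent − S_incident).

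None of these inputs is in the SAP. For illustration only, f is taken from 0.10 to 0.75. S_incident is 0.30 or 0.60, the ends of the range that 5.5 assumes for vital signs and sepsis, borrowed here. S_prevalent is 1.0 (near-miss is itself a vital-sign criterion) or 0.80. Excess in percentage points:

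| f | S_prev 1.0, S_inc 0.30 | S_prev 1.0, S_inc 0.60 | S_prev 0.80, S_inc 0.30 | S_prev 0.80, S_inc 0.60 |
|---|---|---|---|---|
| 0.10 | 7 | 4 | 5 | 2 |
| 0.25 | 17.5 | 10 | 12.5 | 5 |
| 0.50 | 35 | 20 | 25 | 10 |
| 0.75 | 52.5 | 30 | 37.5 | 15 |

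**Step 4. PPV and specificity.** Assume 500 women, 50 outcomes, f = 0.5, S_prevalent 1.0, S_incident 0.50 and specificity 0.75.
- False positives: 450 × 0.25 = 112.5 either way.
- All women: true positives 25 × 1.0 + 25 × 0.5 = 37.5; sensitivity 37.5/50 = 0.75; PPV 37.5/150 = 0.25.
- Incident outcomes only: true positives 12.5; sensitivity 12.5/25 = 0.50; PPV 12.5/125 = 0.10.
- Specificity is 0.75 in both, because the 450 women without the outcome are the same.

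**Step 5. The planned comparison.** Under 5.2 the combined test needs both components positive, so its sensitivity cannot exceed that of vital signs alone. Assume that in incident cases vital signs flag 0.50 and that 60% of those flagged have lactate >2 mmol/L. The difference is 0.50 × 0.6 − 0.50 = −0.20. Add prevalent cases with f = 0.5 and vital signs positive in all of them:
- 90% have lactate >2: 0.5 × (0.9 − 1.0) + 0.5 × (−0.20) = −0.15.
- 60% have lactate >2: 0.5 × (0.6 − 1.0) + 0.5 × (−0.20) = −0.30.

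The bias can go in either direction.

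**Step 6. Horizon.** 5.4 ends at day 14, discharge or death; 7.3 ends at discharge. For a woman still in hospital after day 14 the two differ, and Appendix 1 schedules no assessment after D14.

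**The case against.** The strongest reply is that the SAP nowhere says it will count near-misses already present. Occurrence and prediction can be read as meaning new events, and a protocol that is not at hand may define the window. That is fair as to intent: a reader should not infer that the sponsor chose to count them. But 7.3(c) is the operative text. It carries no restriction where (b) does, and the D0 assessment supplies the data, so an analyst following it would include them.

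Three stronger readings are tempting, and the SAP does not support them.
- **That predictive accuracy as a whole is inflated, or that lactate is favoured.** Specificity does not change, and the vital signs versus vital signs + lactate difference can move either way.
- **That the near-miss list largely repeats the index test.** Only respiratory rate >40 and shock lie wholly inside Table 1 thresholds. Shock must be persistent, and the unconsciousness and oliguria criteria need hours to complete, so some will be met only after the Day 0 reading.
- **That a particular size of bias is established.** Every percentage above rests on assumed inputs.

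It can also be argued that an all-women estimate is useful, since the trigger is meant for every woman with suspected sepsis. That stands, provided the estimate is labelled for what it is and not offered as prediction. The difference in horizon is minor and may be shorthand; aligning the wording settles it.

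**Conclusion.** The point holds. As written, 7.3(c) lets near-misses present at Day 0 count as events that Day 0 tests predicted. The expected consequence is higher sensitivity and PPV for vital signs, with specificity unchanged, and a bias of unknown direction in the planned difference. This assumes that some women are in near-miss at Day 0, which the eligibility criteria make plausible but the SAP does not quantify, and that vital signs flag such women more often than those whose near-miss comes later.

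The size is f × (S_prevalent − S_incident), and f is not given. Over the ranges assumed above the excess in sensitivity runs from 2 to 52.5 points, which shows only that it could be trivial or dominant. The matter should be corrected before analysis. It concerns one exploratory secondary objective; the primary analysis and sample size are not touched.

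**What to change.** In SAP 7.3(c):

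1. Make the predictive analysis the one in women who meet no Appendix 2 criterion at or before the Day 0 index measurement.
2. Count deaths and near-misses first met after that measurement, up to day 14, discharge or death as in 5.4, and align the 7.3 wording to that horizon.
3. Tie the cut-off to the time of the index measurement. Appendix 1 does not give the order of the D0 near-miss assessment and the D0 sample. For criteria that need persistence or duration, state whether onset or completion dates the event.
4. Report women with a near-miss at Day 0 separately, as concurrent diagnosis, with their number, so that f is visible.
5. Keep the all-women version as a labelled sensitivity analysis.

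The cost is SAP wording, since the near-miss assessment is already scheduled daily from D0. The downside is fewer events and wider intervals in an exploratory analysis; how many events would be lost cannot be told from the SAP.

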7.4 HARMS

No adverse events (AEs) are expected to occur due to participation in this study. This is primarily an observational study where an additional blood sample (at two timepoints) are taken by the clinical team to monitor the woman's well-being. There are no other study interventions, which have the potential to create an untoward medical occurrence (AE).

7.5 STATISTICAL SOFTWARE

Statistical analyses will be undertaken using Stata version 17.0 (Stata, College Station, Texas).

Appendix 1: Table of assessments

ASSESSMENT		DAYS IN STUDY													
	Screening		Week 1				Week 2								
Face to face	D0	D1	D2	D3	D4	D5	D6	D7	D8	D9	D10	D11	D12	D13	D14
Study participation															
Eligibility	x														
Informed consent	X														
Eligibility confirmed	X														
Baseline data collection	x														
Vital signs	x	x	x	x	x	x	X	x	х	x	X	X	X	X	X
Medications and fluids	X	x	x	x	x	x	X	x	Х	x	X	X	X	Х	X
Escalation of care	X	x	x	X	x	x	X	Х	Х	x	X	X	X	Х	X
Maternal near-miss criteria assessment	x	x	x	x	x	x	x	х	Х	x	X	X	X	X	X
Blood Sample															
Lactate sample 1 Day 0 (blinded)	X														
Lactate sample 2 Day 1 (22-36 hours) (blinded)		x													
Study completion															
Study completion form															X

Appendix 2: Maternal "near misses"

Status
Brain conditions
Unconscious for more than 12 hours
Stroke
Status epilepticus or uncontrolled fits
Clotting and bleeding
Failure to form clots (clinically absence of clotting from an IV site or suture after 7
minutes, or bedside clotting test taking more than 7 minutes)
Transfusion of more than 2 units of blood
Platelets of less than 50*10^3/µL
Heart conditions
Cardiac arrest
Cardiopulmonary resuscitation
Shock (persistent systolic blood pressure less than 80mmHg with pulse more than
120 beats per minute)
Use of continuous vasoactive drugs e.g. adrenaline infusion
Kidney conditions
Oliguria (urine output less than 30ml/h for 4 hours or less than 400ml/24 hours) not responsive to fluids
Creatinine greater than 300 $\mu mol/L$ or 3.5mg/dL
Dialysis
Liver conditions
Bilirubin more than 100 µmol/L or 6.0 mg/dL
Lung conditions
Cyanosis
Gasping
Respiratory rate more than 40 or less than 6 breaths per minute
Low oxygen saturations of less than 90%% for more than 1 hour
Need for ventilation (not due to anaesthesia)
Uterus conditions
Laparotomy other than for caesarean section or ectopic pregnancy
Hysterectomy due to infection or haemorrhage
Uterine rupture
